### Subject Recruitment and Compensation

- Describe recruitment procedures, including who will introduce the study to potential subjects. Describe how you will ensure that subject selection is equitable and all relevant demographic groups have access to study participation (per 45 CFR 46.111(a) (3)). Include information about approximately how many DUHS subjects will be recruited. If subjects are to be compensated, provide specific prorated amounts to be provided for expenses such as travel and/or lost wages, and/or for inducement to participate.

Potential subjects will be identified via two potential pathways. Research team will screen the outpatient scheduled RHC cases and send a recruitment letter to the subject once their primary care provider has agreed to the study. The subject will be contacted over the phone if the subject has not replied to the letter in at least 10 days per policy. The subject will be provided with any additional information he/she wants. In a second scenario the primary provider approaches the study team with a potential case. In both cases the subject will be notified about being approached on the day of the study about a second approach in person by a health care provider known to the patient for potential consent.

Subjects will be informed that their participation is strictly voluntary. They will be assured that the decision to decline participation will have no impact on their care or the perceptions of their providers.

The subject will be compensated for a total of \$300 for their participation in this clinical study. The subjects will receive \$100 at the following visits: Procedure visit, 2 week follow-up, and 2 month visit.

### Consent Process

- Complete the consent section in the iRIS Submission Form.

### Subject's Capacity to Give Legally Effective Consent

- If subjects who do not have the capacity to give legally effective consent are included, describe how diminished capacity will be assessed. Will a periodic reassessment occur? If so, when? Will the subject be consented if the decisional capacity improves?

Subject has to be able to understand the English language and understand the study process including all potential risk and benefits to the subject. Any subject where the study personnel or treatment team has cause for concern regarding the subject's ability to understand the study process or follow the consent process capacity, will be excluded from the study.

This is a FDA regulated study, therefore, this eConsent platform will comply with 21 CFR Part 11 requirements, which include regulations on electronic records and electronic signatures.

## Study Interventions

- If not already presented in #4 above, describe study-related treatment or use of an investigational drug or biologic (with dosages), or device, or use of another form of intervention (i.e., either physical procedures or manipulation of the subject or the subject's environment) for research purposes.

The study subjects will participate in the following study tests and procedures:

Invasive Test:

1. Regional nerve block under fluoroscopic guidance: A solution of ropivacaine 12 cc (approximately 2.5 teaspoons) and Botox 75-125 units (approximately 0.25 teaspoons), into the space around a nerve, called the splanchnic nerve, which controls the blood vessels in your intestines. These drugs will be delivered using a long needle placed between the patient's ribs in the mid-region of the back. The placement of the needle will be performed by an anesthesiologist experienced with the needle placement, with the assistance of x-ray guidance. The subject's measurement will be monitored for 60 minutes post-block.
2. Cardiopulmonary exercise: The subject will exercise by pedaling on a bike in a supine position for about 2-5 minutes, before stopping to rest. The catheter will remain in the subject's heart to measure pressures while exercising to provide information about the subject's exercise ability.

Non-Invasive Tests:

1. Vital Signs (Orthostatic vital signs)
2. Imaging with ultrasound, impedance, radiofrequency
  1. Fluid content in the body and lungs: The subject will wear a vest that emits radiofrequency waves to measure fluid content (ReDs Vest). The InBody uses Bioelectrical Impedance Spectroscopy to determine fluid content in the subject's body.
  2. Lung impedance: electrodes will be attached to the subject's upper back and chest to determine the intra-thoracic blood volume (CardioSet)
  3. Arterial stiffness using a brachial cuff. A cuff will be applied to your arm, similar to a blood pressure cuff, and a hand held probe will be placed on your groin and arm. The cuff will inflate and will measure pulse wave changes in your blood vessels (Sphygmocor)
  4. Cardiac Hemodynamics: the PhysioFlow device measures the subject's cardiac output, stroke volume, systemic vascular resistance and left cardiac work index.
  5. Oxygen Utilization: VO2 Master Pro (Oxygen consumption) will be used to measure oxygen consumption during rest and exercise. PortaLite and MOXY will measure oxygen concentration during exercise.
  6. Heart Rate Variability: The WHOOP strap 3.0 will measure heart rate and heart rate variability and will be worn for approximately one hour.
3. 6 minute walk test to measure your exercise capacity and endurance.
4. Questionnaires about the subject's feeling about their shortness of breath and breathing at rest
5. Cardiopulmonary (CPX) Testing: Exercise testing with the subject using an upright bike. The subject will exercise at their maximum effort. The subject will be monitored for exercise intolerance, shortness of breath, or pain in the chest. The subject will wear a face mask to measure oxygen intake and carbon dioxide output.
6. MUGA Scan: non-invasive imaging method to evaluate the function of your heart. This scan will help determine more information about the health of the subject's cardiac ventricles and blood distribution.

Laboratory Tests:

1. Blood Volume Analysis: Administration of a small amount of plasma protein, albumin, containing a small amount of radioactive iodine (injected through the PIV). The radioactive iodine labeled albumin

protein (blood volume solution) will be administered through the PIV line. Blood samples will be withdrawn before administration of the blood volume solution and 12, 16 and 20 minutes after administration. The blood samples will be processed at the Duke Nuclear Laboratory using the Daxor Analyzer for further processing

2. Biomarkers: Blood samples will be taken before the procedure and after the procedure for analysis of NT pro-BNP (indication of worsening heart failure) and CA-125 (indication of inflammation).
3. Autonomic Nervous System regulators: Blood samples will be taken in the catheterization lab before and after the splanchnic block. The samples will be processed and sent out to labs that specialize in analyzing these samples for hormones angiotensin II, vasopressin, catecholamines, and metanephrines.

### Risk/Benefit Assessment

- Include a thorough description of how risks and discomforts will be minimized (per 45 CFR 46.111(a) (1 and 2)). Consider physical, psychological, legal, economic and social risks as applicable. If vulnerable populations are to be included (such as children, pregnant women, prisoners or cognitively impaired adults), what special precautions will be used to minimize risks to these subjects? Also identify what available alternatives the person has if he/she chooses not to participate in the study. Describe the possible benefits to the subject. What is the importance of the knowledge expected to result from the research?

Procedural risks of splanchnic nerve blocks have been extensively studied. Risks associated with this anesthetic nerve block are uncommon. Patients undergoing this procedure have a small risk (<1%) risk of developing local anesthetic systemic toxicity as a complication of regional anesthesia. Symptoms include non-specific central nervous system effects (altered mental status, agitation, seizures) and cardiac arrest. We have now completed 28 cases in the first pilot trial using lidocaine/ropivacaine and found no acute or chronic complications.

Mild complications like local pain at injection site, orthostatic hypotension and gastrointestinal dysmotility are time limited and improve with resolution of the anesthetic block. Severe complications like pneumothorax possibly requiring a chest tube, aortic vessel puncture with retroperitoneal bleed or hematothorax and spinal cord injury with possible paralysis. These are very rare since placement of the needle occurs under fluoroscopic guidance.

Other minor risks can include (in order of report in literature and experience at Duke):

1. Pain at puncture site and intercostal neuralgia
2. Gastrointestinal dysmotility including diarrhea, constipation and abdominal cramping as well as nausea
3. Bleeding at puncture site

We will perform the splanchnic block for chronic heart failure, which is a new indication. The splanchnic nerve block has now been studied by us for acute /chronic heart failure but not been studied in the setting of chronic disease. We do not expect unexpected side effects other than stated above but unexpected side effects cannot be excluded. For safety purposes subjects enrolled in this study will remain monitored for several hours after the SNB and re-examined at 2 weeks.

Anticipated benefits to the subject include improvement in central vascular congestion with a reduction in cardiac preload and pulmonary arterial pressures as well as left sided filling pressures. A reduction in cardiac pressures is also likely to improve symptoms of congestion, including shortness of breath.

Further it is expected that a decongestion of the central veins and interruption of the cardiorenal reflex loop will result in an improvement in renal function as measured by urine output. This will further contribute to the decongestion of the subject's vasculature.

While both of those effects are only temporary (up to 6 months, the benefit provided by the brief episode of decongestion can provide lasting symptomatic improvement.

Given prior pilot studies and theoretical framework we expect a symptomatic improvement of patients during the nerve block. Given that we have not seen any side effects in acute heart failure patients after the nerve block wore off we do not expect comparable effects in chronic heart failure patients when their block wears off given similar pathophysiology.

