Dose down titration scheme is as following: If BP is too low (newly <90mmHg, independent of heart failure medication changes done clinically) or patient report orthostatic symptoms we will return for the next patient to the preceding lower Botox dose. If symptoms of orthostasis or hypotension are experienced already at the lowest dose we will drop the injection dose to 50 Units (not more than 1.5U/kg) . The effects of ropivacaine are expected to occur as early as 15 minutes and last for 24h. The acute effects will serve as confirmation of procedural success and provide reassurance that BTX was injected in the right location. BTX is a neurotoxin that blocks cholinergic neurotransmission and offers temporary autonomic modulation via ganglionic block. The peak pharmacological properties of BTX are expected at 2 weeks post injection. The estimated duration of BTX effect is up to 4-6 months.

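### The risk section ties recovery from orthostatic hypotension and gut dysmotility to the local anesthetic and omits botulinum toxin, and the 6-month record screen is worded for traumatic complications only.

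*Combined protocol and SAP*

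**What the plan says.** The Risk/Benefit Assessment lists injection-site pain, orthostatic hypotension and GI dysmotility as mild complications that "are time limited and improve with resolution of the anesthetic block". Its own safety experience is with the local anesthetics: "We have now completed 28 cases in the first pilot trial using lidocaine/ropivacaine and found no acute or chronic complications". The follow-up it describes is that subjects "will remain monitored for several hours after the SNB and re-examined at 2 weeks". Neither the risk nor the benefit paragraphs of that section name BTX. The benefit paragraphs do allow a long course, but for the expected benefits: "While both of those effects are only temporary (up to 6 months".

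The nerve block text under Testing procedures describes two drugs with different time courses. For the anesthetic: "The effects of ropivacaine are expected to occur as early as 15 minutes and last for 24h". For BTX: "The peak pharmacological properties of BTX are expected at 2 weeks post injection", and "The estimated duration of BTX effect is up to 4-6 months". The dose-reduction rule in the same place says that if blood pressure is newly below 90 mmHg "or patient report orthostatic symptoms we will return for the next patient to the preceding lower Botox dose".

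Data & Safety Monitoring has two relevant sentences. One names hypotension, worsening renal function and clinical deterioration, to be recorded after each subject completes the intervention, with no end date. The next adds a screen of the electronic medical record at 2 weeks and 6 months, and that screen is for traumatic complications of the block.

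**The concern.** What is new in this study is a prolonged block with a long-acting agent, and Study design gives safety and BTX dose finding among its purposes. The risk section nevertheless describes recovery as if only the short-acting drug had been injected. Someone weighing the risk from that section would take orthostatic and GI effects to be over in about a day.

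The section also gives the two sides different clocks: benefit may last up to 6 months, while these harms end with the anesthetic. Background & Significance attributes orthostatic hypotension after the block to greater splanchnic storage capacity, which is the mechanism from which the benefit is expected. If BTX prolongs one, the text gives no reason why it could not prolong the other.

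At stake are an accurate statement of risk for the study drug and what a safety pilot learns about late autonomic effects. A 6-month record screen limited to trauma would not look for hypotension or GI events, although it falls while BTX may still be active or has only just stopped acting.

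**Working it through.** There is no sample size, power or error-rate figure to reproduce. The check sets the protocol's stated time courses side by side, with injection as day 0.

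**Inputs**
- Ropivacaine effect: 24 h (Testing procedures), so it ends at day 1.
- BTX peak: 2 weeks (Testing procedures), so 2 × 7 = day 14.
- BTX effect: up to 4-6 months (Testing procedures). With 30.44 days per month (an assumption), 4 × 30.44 = 121.8 days and 6 × 30.44 = 182.6 days. Both are maxima, and both describe drug effect, not side effects.
- Side effects of permanent block: limited to 48 h (Background & Significance; non-HF patients, surgical or alcohol block), so they end at day 2.

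**Comparison**
1. End of anesthetic effect to BTX peak: 14 − 1 = 13 days. Resolution of the anesthetic therefore says nothing about effects arising as BTX approaches its peak.
2. End of the 48 h limit to BTX peak: 14 − 2 = 12 days. That limit counts from the procedure, so it too ends before the peak. It bears on how long effects last once they start, but cannot be read directly as a limit on BTX effects.
3. The protocol's own attribution: low blood pressure or orthostatic symptoms send the next patient back to the preceding lower Botox dose, or to 50 units if they occur at the lowest dose. A rule that changes the BTX dose for these symptoms treats them as possible BTX effects. The risk section's account of recovery does not.
4. The 6-month screen: 6 months is day 182.6, the upper end of the stated BTX effect. A record review at that point can look back over the whole stated period. As worded, it would look only for trauma.
5. Onset near the peak: the 2-week re-examination falls on day 14, and Table 1 schedules orthostatic vitals at follow-up visits. The table is broken, so the last of these reads as week 4 or week 8. On either reading, orthostatic effects that start near the peak fall within scheduled checks, and dose steps rest on the 4-week assessment.

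**The case against.** The strongest reply is that the gap lies in one section and not in the plan. The BTX time course and a BTX-specific response to orthostasis are stated under Testing procedures. The disputed sentence follows text about the anesthetic block and can be read as describing that component. The section also says that unexpected side effects cannot be excluded. This stands to the extent that the sentence is incomplete rather than false. It remains incomplete in the place where risk is set out.

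The second reply is the 48 h experience with permanent block: a lasting block need not mean lasting side effects. This is real evidence against long persistence and belongs in the text. It does not rescue the present wording, which rests on the anesthetic wearing off. It also comes from non-HF patients with surgical or alcohol block. The BTX support beside it is one reported case of refractory hypertension.

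The third concerns monitoring. The trauma screen is an addition to the recording of hypotension, renal function and deterioration, which has no end date. Adverse event reports go to the IRB under its policy, and Table 1 has late phone calls. All of this stands.

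A reader might therefore go too far by subtracting week 8 (day 56) from the BTX maximum: 121.8 − 56 = 65.8 and 182.6 − 56 = 126.6, or about 66-127 days, and calling that an unmonitored window. The documents do not support this. The figures are a calendar ceiling on drug effect and may be zero for side effects, and other recording continues through that time.

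**Conclusion.** The point holds in a limited form. The risk section states a recovery time that fits the 24 h anesthetic, does not mention the agent with a 2-week peak and up to 4-6 months of effect, and sits badly with the protocol's own dose-reduction rule. The 6-month record screen is narrower than a safety and dose-finding pilot needs, given that hypotension, renal function and deterioration have no 6-month time point elsewhere.

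The size is modest: one statement of risk and the scope of one planned search. Three further inferences are not supported:
- That BTX side effects last 4-6 months. No section gives a duration for side effects; the figure is for drug effect.
- That GI or orthostatic symptoms are never asked about. One row of Table 1 with a month-6 mark lost its label in extraction and may be such a check.
- That dose escalation is compromised. It uses the 4-week assessment, after the expected peak.

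The conclusion assumes that the risk section is complete as shown. The consent pages were removed, so nothing is inferred about what subjects are told there.

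**What to change.** 1. In the Risk/Benefit Assessment, limit the sentence on recovery to the local anesthetic (about 24 h). Add that orthostatic and GI effects related to BTX could appear later, around its 2-week peak. State that their duration in heart failure is unknown and could extend over the period of BTX effect (up to 4-6 months), and that experience with permanent block in non-HF patients suggests 48 h.
2. In Data & Safety Monitoring, widen the existing 6-month record screen from traumatic complications to include hypotension or orthostasis, worsening renal function, clinical deterioration and GI events.

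The cost is a few sentences and a slightly longer search in a review already planned; no visit is added. The wider screen will still find only events that reached the record, so it will miss mild symptoms that were never reported.

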### Costs to the Subject

- Describe and justify any costs that the subject will incur as a result of participation; ordinarily, subjects should not be expected to pay for research without receiving direct benefit.

All testing and services performed only for the purposes of the clinical study will be provided at no cost to the research subject. However, the subject or the subject's health insurance or Medicare is responsible for all costs that are part of usual medical care that would have happened if the subject were not in the clinical study. If the subject's health insurance or Medicare requires any co-payment, co-insurance, or deductible, the subject will be responsible for making that payment. Anything not paid by either the study sponsor or the subject's health insurance company will be billed directly to the subject for payment.

### Data Analysis & Statistical Considerations

- Describe endpoints and power calculations. Provide a detailed description of how study data will be analyzed, including statistical methods used, and how ineligible subjects will be handled and which subjects will be included for analysis. Include planned sample size justification. Provide estimated time to target accrual and accrual rate. Describe interim analysis including plans to stop accrual during monitoring. Phase I studies, include dose escalation schema and criteria for dose escalation with definition of MTD and DLT.

[name] in the Duke Heart Center will be performing the statistics for the Splanchnic III study. We will perform descriptive statistics. Statistical comparisons will be made using t-tests for continuous outcomes and chi square or Fisher's exact test. Unless otherwise specified, a two-sided 0.05 level of significance will be used to declare change in pre-and post-procedure variables different.

There is no direct measure of technical success following attempted block of the splanchnic nerves. Procedural success to block the splanchnic nerves will be assumed in 70% of the cases based on the experience in splanchnic nerve blocks in patients with intractable cancer.

### Data & Safety Monitoring

- Summarize safety concerns, and describe the methods to monitor research subjects and their data to ensure their safety, including who will monitor the data, and the frequency of such monitoring. If a data monitoring committee will be used, describe its operation, including stopping rules and frequency of review, and if it is independent of the sponsor (per 45 CFR 46.111(a) (6)).

Due to the experimental nature of this intervention, data will be recorded after each subject completes the intervention for signs of unintended negative effects. These include hypotension, worsening renal function, or clinical deterioration. Additionally, subject's electronic medical data will be screened for any traumatic complications from the nerve block at 2 weeks, and 6 months post-procedure.

Unanticipated severe adverse events will be reported to the IRB per IRB policy.

In accordance with federal regulations the PI will monitor for review, and promptly report to the IRB, appropriate institutional officials, sponsor, coordinating center and the appropriate regulatory agency head, all unanticipated problems involving risks to subjects or others that occur in the course of a subject's participation in research study, in accordance with (45 CFR 46.103(b)(5)(i) and 21 CFR 56.108(b)(1)), all AE reports will be reported per the DUHS IRB policies.

#### **Privacy, Data Storage & Confidentiality**

- Complete the Privacy and Confidentiality section of the iRIS submission form.

#### **Describe Role of External Personnel:**

N/A
